14.3 Vital Signs, Height, Weight, and BMI

Vital signs, height (as measured by a stadiometer) and weight are assessed at Screening and Baseline, at all visits from Week 1 through Week 6, and at unscheduled visits. BMI will be derived as Weight (kg)/ [Height (m)]². Height and weight measurements are optional at the Week 2 and Week 5 visits if these are conducted remotely.

Vital signs, height, weight, and BMI will be summarized by treatment group using descriptive statistics at Baseline and all post-baseline visits. The change from Baseline values will also be summarized by treatment group at the post-baseline visits.

Vital sign and weight values will be considered PCI if they meet both the observed value criteria and the change from baseline criteria listed in Table 4. The number and percentage of subjects with post-baseline PCI values will be summarized by treatment group at each post-baseline visit and for overall post-baseline. For the overall post-baseline summaries, all post-baseline values will be considered, including unscheduled and out of window values. Subjects with multiple PCI values for a given parameter will be counted only once for that parameter. For the by-visit summary, the numerator for the percentage is the number of subjects with a post-baseline PCI value for the given parameter, visit and treatment group, and the denominator is the number of subjects with non-missing values for the given parameter, visit and treatment group. For the overall post-baseline summary, the numerator for the percentage is the number of subjects with at least one post-baseline PCI value for the given parameter and treatment group, and the

denominator is the number of subjects with at least one post-baseline value for the given parameter and treatment group. A listing of all subjects with any PCI values will be provided.

Table 4 Criteria for Potentially Clinically Important Vital Signs

		Criteria ^a						
Vital Sign Parameter	Unit	Observed Value	And/Or	Change Relative to Baseline				
Systolic blood pressure	mama II ca	≥140	And	Increase of ≥20				
(supine or sitting)	mmHg	≤70	And	Decrease of ≥20				
Diastolic blood pressure	ana II o	≥90	And	Increase of ≥15				
(supine or sitting)	mmHg	≤50	And	Decrease of ≥15				
D-1 (ii4i)	1	≥120	And	Increase of ≥15				
Pulse (supine or sitting)	bpm	≤50	And	Decrease of ≥15				
Weight	Va	Not Applie	abla	Increase of ≥7%				
Weight	Kg	Not Applic	aute	Decrease of ≥7%				

A post-baseline value is considered as a PCI value if it meets both criteria for observed value and change from baseline.

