4.1 Inclusion Criteria

A subject must meet all of the following inclusion criteria at Screening and Baseline to be eligible for participation in the study:

Study Population

- 1. Is a male or female 5 through 17 years of age at Screening and Baseline visits
- 2. Is within the 5th to 95th percentile for gender specific weight for-age and height-for-age growth charts from the National Center for Health Statistics
- 3. Informed consent prior to the conduct of any study procedures is required as follows:
 - a. The subject should provide written or oral assent if deemed able by the Investigator.
 - b. The subject's parent/legally acceptable representative (LAR) must provide written consent. The subject's parent/LAR must be considered reliable by the Investigator, able to complete assessments regarding the subject's development and behavior throughout the study, and able to help ensure compliance with study treatment, study visits, and protocol procedures
 - c. If a person other than the parent/LAR has been designated as a caregiver for the purpose of providing input for caregiver-reported scales, that person must also provide written consent. Such a designee should be a family member, adult and responsible, living with or in very frequent contact with the subject participating in the study, who is committed to providing responses for the caregiver-reported scales for the duration of the study.

Final Version: 1.0

Study: ACP-103-069 Clinical Study Protocol Amendment 4 Date: 21 December 2022

The process of obtaining informed consent will be conducted in accordance with institutional review board (IRB) or ethics committee (EC) policy and applicable local law.

- 4. In the Investigator's opinion, the subject to the best of his/her ability, the parent/LAR, and the designated caregiver (if applicable, and in accordance with IRB or EC policy and applicable local law) are able to understand the nature of the study, follow protocol requirements, and be willing to comply with study drug administration requirements
- 5. Is able to swallow the test placebo capsule without difficulty during the Screening or Baseline visits
- 6. Has a mental age of ≥ 2 years as determined by Investigator based upon school evaluation social history or medical records documented at any time before or at Screening

Psychiatric Diagnosis and Concomitant Medications

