- 16. For age <13 years, a resting position (sitting or supine) systolic (SBP) and/or diastolic blood pressure (DBP) level ≥90th percentile for gender-specific age and height charts from the National Heart and Lung Institute (NHLI), at Screening or Baseline. For age ≥13 years a resting position (sitting or supine) SBP ≥120 mmHg and/or a DBP ≥80 mmHg, at Screening or Baseline.
- 17. Has a clinically significant abnormal ECG at Screening or at Baseline.
- 18. Has a history or presence on at least one ECG at Screening or at Baseline, of any of the following cardiac conduction abnormalities:
 - a. QTcF \geq 450 ms
 - b. PR interval >220 ms
 - c. Evidence of second- or third-degree atrioventricular block
 - d. Evidence of complete left bundle branch block
 - e. Intraventricular conduction delay with QRS >110 ms
 - f. QRS or T wave morphology that could, in the Investigator's opinion, render QT interval assessment unreliable
 - g. Sick sinus syndrome
 - h. Non-sinus rhythm

Final Version: 1.0

i. Resting heart rate <50 beats per minute

For the Baseline visit, the decision to allow study entry should be based on the Investigator's interpretation of the ECG tracing collected on the study-provided ECG device during the visit and that the QTcF interval is not exclusionary.

One repeat set of triplicate ECGs is allowed that can occur either at Screening or Baseline.

- 19. Has a known family or personal history or symptoms of long QT syndrome or has a history of cardiac arrhythmias or risk factors for torsade de pointes and/or sudden death, including symptomatic bradycardia, hypokalemia or hypomagnesemia, and the presence of congenital prolongation of the QT interval
- 20. Has a known history of hepatitis B virus (HBV), hepatitis C virus (HCV), or human immunodeficiency virus (HIV). Subjects with a history of hepatitis B are eligible if there is documentation of a negative test for hepatitis B surface antigen and a positive test for antibodies to the HBV surface antigen. Subjects with a history of hepatitis C are eligible if there is documentation of a negative HCV RNA test.
- 21. The subject, or any member of the household, has suffered from coronavirus disease 2019 (COVID-19) or had a COVID-19 (PCR or immunoglobulin) positive test in the last 4 weeks before Screening
- 22. Has had greater than 10% blood loss within 60 days prior to study drug administration

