6.4.3 Vital Signs

Vital signs will include body temperature, resting respiration rate, sitting (or supine) systolic and diastolic blood pressure, and pulse rate.

The sitting (or supine) blood pressure should be measured after the subject has been sitting (or supine) for ≥ 3 minutes. If the initial blood pressure measurement is:

- ≥90th percentile systolic and/or diastolic for gender-specific age and height charts from the National Heart and Lung Institute (NHLI) for subjects under 13 years or
- \geq 120 mmHg systolic or \geq 80 mmHg diastolic for subjects 13 through 17 years,

at least 5 minutes rest should be allowed after the first measurement; then two additional blood pressure measurements are to be performed consecutively. The average of the three blood pressure measurements, systolic and diastolic, is the final blood pressure measurement and this average is the one to be entered into the EDC. All of the three blood pressure measurements with documentation of the time starting the resting and the time at which the two additional blood pressures are measured should be source documented.

If the subject is reporting symptoms of orthostatic hypotension when standing up after the blood pressure measurement, then the subject will be asked to lie down for 5 minutes, blood pressure and pulse rate will be measured, then the subject will be asked to stand and blood pressure and pulse rate measurements will be repeated after standing 1 to 3 minutes in order to measure the severity of the orthostatic hypotension. Vital signs will be collected at Screening and Baseline, at all visits from Week 1 through Week 6, and at unscheduled visits. Vital signs are optional at the Week 2 and Week 5 visits if these are conducted remotely.

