Appendix F Criteria for Potentially Clinically Important Vital Signs

Vital Sign Parameter	Unit	Criteria		
		Observed Value	And/Or	Change Relative to Baseline
Systolic blood pressure (supine or sitting)	mmHg	≥140	And	Increase of≥20
		≤70	And	Decrease of≥20
Diastolic blood pressure (supine or sitting)	mmHg	≥90	And	Increase of≥15
		≤50	And	Decrease of ≥15
Pulse (supine or sitting)	bpm	≥120	And	Increase of≥15
		≤50	And	Decrease of≥15
Weight	kg	Not Applicable		Increase of ≥7%
				Decrease of ≥7%

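### The potentially clinically important (PCI) blood pressure count uses one 140/90 limit for ages 5 to 17, so it is insensitive to marked rises in individual children, mainly for systolic pressure and under age 13

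*SAP*

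**What the plan says.** The trial enrols ages 5 through 17 (Protocol Section 4.1: "Is a male or female 5 through 17 years of age at Screening and Baseline visits"). Protocol Appendix F, "Criteria for Potentially Clinically Important Vital Signs", sets the high SBP rule as "≥140 And Increase of≥20" and the high DBP rule as "≥90 And Increase of≥15", with no split by age. SAP Table 4 repeats these limits. SAP Section 14.3 makes the rule conjunctive: "Vital sign and weight values will be considered PCI if they meet both the observed value criteria and the change from baseline criteria". The table's footnote says the same: "A post-baseline value is considered as a PCI value if it meets both criteria for observed value and change from baseline".

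Two other places in the protocol apply age bands to the same subjects:

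- Exclusion criterion 16 (Section 4.2) bars children under 13 at or above the 90th percentile for sex, age and height. For older subjects the bar is "For age ≥13 years a resting position (sitting or supine) SBP ≥120 mmHg and/or a DBP ≥80 mmHg", at Screening or Baseline.
- Section 6.4.3 requires repeat readings on the same bands: "≥90th percentile systolic and/or diastolic for gender-specific age and height charts" under 13, and 120 systolic or 80 diastolic from 13 through 17.

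SAP Section 14.3 also summarises observed vital signs and their changes from Baseline by arm at every post-baseline visit. Under SAP Section 5.1 those summaries include the minimum and maximum.

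**The concern.** A PCI table exists to count individuals with a marked abnormal change, which means cannot do. In this plan it is the only categorical summary of blood pressure, and the listing of flagged subjects in SAP Section 14.3 uses the same limits. If the observed-value limit lies far above where the subjects start, the change criterion has little or no role and most marked rises go uncounted.

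For example, a 14-year-old who goes from 105 to 138 mmHg has risen by 33, well over the stated 20, and is not counted. Vital signs are a named safety endpoint and safety is assessed descriptively only, so a low count in each arm could be given more weight than it can bear.

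**Working it through.** **Figures in the plan.** The documents give no calculation behind the blood pressure limits, so there is none to reproduce. The share of younger children does reproduce: 0.35 × 228 = 79.8, stated as 80.

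**1. Rise needed for a flag.** This follows from the limits:

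- SBP: rise needed = max(140 − baseline, 20)
- DBP: rise needed = max(90 − baseline, 15)

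**2. Ages 13 to 17, from the documents alone.** Criterion 16 leaves baseline SBP below 120 and DBP below 80.

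| Baseline | Rise needed |
|---|---|
| SBP 119 | 140 − 119 = 21 |
| SBP 105 | 140 − 105 = 35 |
| DBP 75 to 79 | 15 (the change criterion decides) |
| DBP 65 | 90 − 65 = 25 |
| DBP 60 | 90 − 60 = 30 |

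For SBP, 140 − baseline exceeds 20 at every permitted baseline, so the 20 mmHg condition never binds. For DBP it does bind at 75 to 79.

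**3. Ages 5 to 12.** The percentile values are not in the documents. At assumed SBP baselines of 85 to 110, the rise needed runs from 140 − 85 = 55 down to 140 − 110 = 30.

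**4. Share of marked rises that the rule catches (simulation; all distributions assumed).** Baseline is normal and truncated at the entry limit, and change is normal.

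| Group | Assumptions | Share flagged |
|---|---|---|
| SBP rises ≥20, ages 5–12 | mean baseline 95–103, change SD 8–12, mean rise 0–10 | about 0–10% |
| SBP rises ≥20, ages 13–17 | mean baseline 105–110, same changes | about 5–27% |
| DBP rises ≥15, ages 5–12 | mean baseline 60–63, change SD 7–9, mean rise 0–10 | about 1–18% |
| DBP rises ≥15, ages 13–17 | mean baseline 65–70, same changes | about 14–48% |

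**5. Comparison with the protocol's own 120 limit, SBP, ages 13 to 17.** Assumed: baseline mean 105, SD 8, truncated below 120; mean rise 8; change SD 8 to 12. Per visit, the present rule flags 0.4% to 2.4%. An observed value of at least 120 with the same rise of at least 20 flags 5.6% to 14%.

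**6. Overall post-baseline count.** SAP Section 14.3 also counts subjects with any flagged value. The step 5 assumptions were run over six visits, with an assumed between-visit correlation of 0.3 to 0.7. The present rule flags about 1.4% to 10.5% with the 8 mmHg shift and about 0.1% to 2.7% without it. With no shift, the 120-plus-20 rule flags about 2% to 19%.

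**7. Would a mean shift be seen elsewhere?** The standard error of an arm difference is SD × √(2/n). With SD 12 and n = 64 it is 2.12, and 8/2.12 = 3.8. With SD 8 and n = 76 it is 1.30, and 8/1.30 = 6.2. A shift of this size would be plain in the change-from-Baseline table.

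**The case against.** A reader might infer that the safety output is nearly blind to blood pressure rises, or that the table will be close to zero in every arm whatever the drug does. The documents do not support this. Observed values and changes are summarised by arm at each visit, with maxima (step 7). A clinically significant rise can also be reported as an adverse event. The overall PCI count does respond to a shift (step 6), and the DBP criterion works as written for adolescents at 75 to 79.

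A reader might also infer that an entry limit of 120 and a PCI limit of 140 contradict each other. They need not, because PCI limits sit above entry limits elsewhere. QTcF is excluded at 450 ms or more and is PCI above 500. ALT and AST are excluded above 2 times the upper limit of normal and are PCI from 3 times. In Section 6.4.3 the age bands only trigger repeat readings.

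Two further points stand. Hypertension is not among the class effects listed for active monitoring in Protocol Section 6.4. An age-banded row also costs specificity (step 6).

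What survives is narrower. The protocol recognises that one blood pressure limit does not fit ages 5 to 17, yet its only count of individual rises uses one, without a stated reason.

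**Conclusion.** The point holds for the PCI count, not for the safety output as a whole. The count is insensitive to individual marked rises, most clearly for SBP and for ages 5 to 12, and less so for adolescent DBP. The SBP arithmetic for ages 13 to 17 rests on the documents alone, for subjects who met criterion 16. The 30 to 55 mmHg range for younger children and every flag rate rest on assumed distributions, because the percentile values and the variability of blood pressure are not given.

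The SAP copies Appendix F faithfully, so the mismatch lies between Appendix F with Table 4 on one side and criterion 16 with Section 6.4.3 on the other. No efficacy conclusion is affected. This is an inexpensive improvement to consider.

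**What to change.** Reconcile the passages in the tabulation. In SAP Section 14.3 and Table 4, add descriptive high blood pressure rows that combine the age-banded limits already in the protocol (90th percentile for sex, age and height under 13; 120 or 80 mmHg from 13 through 17) with the existing change criteria (20 systolic, 15 diastolic). Show them overall and by age stratum, and keep the 140/90 row. State which age assigns a subject to a band and which percentile charts are used. This concerns tabulation only, not patient management.

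The cost is SAP wording and programming. Age, sex, height and blood pressure are already collected, and the charts are already needed for eligibility. There is precedent: SAP version 3.0 revised the PCI cut-offs for phosphate and urinalysis (Appendix 21.4).

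The downside is more flagged values and lower specificity: about 2% to 19% of adolescents over six visits with no drug effect, under the assumptions in the working. The rows should therefore be read as a comparison between arms, not as absolute rates. SAP Section 19 now states that nothing differs from the protocol analyses, so the addition should be noted there.

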14.4 Electrocardiogram (ECG)

Electrocardiogram is performed at Screening, Baseline, Week 3, and Week 6 visits.

All tracings will be evaluated by a central reading laboratory. At the Baseline visit, the machine-read results will also be recorded. All data, including the machine-read Baseline results, will be listed. ECG data summaries will be performed using the centrally evaluated data.

Observed values of ECG variables (heart rate, PR interval, RR interval, QRS interval, QT interval, and QTc intervals) and the changes from baseline at each assessment timepoint will be summarized by treatment group. QTc intervals include QTcB (Bazett's formula) and QTcF (Fridericia's formula).

QTcF will also be categorized into the following categories (msec) and the number and percentage of subjects in each category will be summarized by treatment group at each visit and for the overall post-baseline maximum:

- Observed: ≤ 450 , 451 to 480, 481 to 500, and ≥ 500
- Change from Baseline: ≤ 10 , 11 to 30, 31 to 60, and ≥ 60

For cardiologist's interpretations, the number and percentage of subjects with ECG results that are determined as normal or abnormal will be summarized at scheduled visits. The overall post-baseline worst interpretation will also be summarized (i.e., if a subject has one or more post-baseline ECG results that is/are considered as abnormal, this subject will be counted in the abnormal category). Cardiologist's interpretations will also be summarized in a shift table to determine the number and percentage of subjects with ECG results classified as normal or abnormal at scheduled post-baseline visits relative to the same classification at the Baseline visit. The shifts from Baseline to overall post-baseline worst interpretation will also be presented. For the by-visit shift summary, the denominator is the number of subjects with non-missing cardiologist's interpretation at Baseline and the given visit for the given treatment group. For the summaries of shift from Baseline to the overall post-baseline worst interpretation, the denominator is the number of subjects with non-missing Baseline and at least one post-baseline cardiologist's interpretation for the given treatment group.

Electrocardiogram variable values will be considered as PCI values if they meet or exceed the upper limit values listed in Table 5. The number and percentage of subjects with post-baseline PCI values will be summarized by treatment group at each post-baseline visit and for overall post-baseline. For the by-visit summary, the numerator for the percentage is the number of subjects with a post-baseline PCI value for the given parameter, visit and treatment group, and the denominator is the number of subjects with non-missing values for the given parameter, visit and treatment group. For the overall post-baseline summary, the numerator for the percentage is the number of subjects with at least one post-baseline PCI value for the given parameter and treatment group, and the denominator is the number of subjects with at least one post-baseline value for the given parameter and treatment group. A listing of all subjects with any PCI values will be provided.

 Table 5
 Criteria for Potentially Clinically Important ECG Values

ECG Parameter	Unit	High PCI Criteria
QRS Interval	msec	≥120
PR Interval	msec	≥220
QTcB or QTcF	msec	>500
QTcB or QTcF: change from baseline	>60 msec	

14.5 Physical Examination

Physical examination is performed at Screening, Baseline, Week 3 and Week 6 visits.

Physical examination results (normal, abnormal, and not done) at Baseline and all scheduled post-baseline visits will be summarized in a frequency table by treatment group, body system and visit.

A listing of physical examination data will be provided.

14.6 Syncope and somnolence

Syncope and somnolence are assessed at Screening and Baseline, at all visits from Week 1 through Week 6, and at unscheduled visits. Occurrences syncope and somnolence should be reported as adverse events.

Subject history of syncope, family history of syncope, subject history of somnolence will be summarized as Baseline Disease Characteristics. Incidences of syncope and somnolence during the study will be summarized as TEAEs.

Assessment of syncope and somnolence at each visit will be listed.

14.7 Other Safety Variables

14.7.1 Columbia-Suicide Severity Rating Scale (C-SSRS)

For the C-SSRS, the number and percentage of subjects with suicidal ideation or behavior during the study will be tabulated.

For calculating the percentages, the denominator will be the number of subjects with at least one post-baseline C-SSRS.

14.7.2 Extrapyramidal Symptom Rating Scale–Abbreviated (ESRS-A)

ESRS-A total scores and the four individual global clinical global impression movement severity scores will be summarized by treatment group using descriptive statistics at Baseline and each post-baseline visit. The change from Baseline values will also be summarized by treatment group at the post-baseline visits.

15 CLINICAL PHARMACOKINETIC AND PHARMACODYNAMIC ANALYSES

Plasma concentration data for pimavanserin and its metabolite (AC-279) will be listed and summarized using standard summary statistics.

If data allow, population PK and PK/PD analyses will be performed to further characterize the PK profile and exposure response relationship of pimavanserin and its metabolite using measures of safety, and efficacy parameters. The results of population PK and PK/PD modeling will be presented in a separate report. Pimavanserin plasma concentration data will remain blinded to the

Investigators and Sponsor study team until the unblinding of the clinical database at the end of the study.

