1.3.2 Phase 1 Study in Adolescents With Psychiatric Disorders

The PK profile of pimavanserin was evaluated in a Phase 1, open-label, multiple ascending dose (10, 20, or 34 mg) study in adolescents (male or female adolescents between 13 and <18 years) with psychiatric disorders (ACP-103-050). When adjusted for weight at Baseline, pimavanserin steady state systemic exposure was approximately dose proportional over the studied dose range (10 to 34 mg). There were no consistent differences in pimavanserin or AC-279 C_{max-ss} and AUC_{τ} between the age subsets; however, small differences observed were likely due to weight and not age. Accumulation of pimavanserin (approximately 3- to 5-fold overall) and AC-279 (approximately 13- to 18-fold) is consistent with adults and was expected based on the known respective half-lives (57 hours and 200 hours) relative to dosing interval. The parent (pimavanserin) to metabolite (AC-279) steady state ratio for C_{max-ss} and AUC_{τ} was comparable across dose cohorts and ranged from 120% to 151%. These values are comparable to those in adults confirming the lack of difference in metabolism between adults and adolescents.

Additional information on previous pimavanserin clinical studies is provided in the pimavanserin Investigator's brochure and in the US package insert for NUPLAZID® (pimavanserin) for oral use.

Study Rationale

Irritability associated with ASD is often caused by multiple underlying comorbid conditions, many of which are linked to serotonergic system dysfunction. Based on the efficacy of two approved antipsychotics with 5-HT_{2A} antagonism (and inverse 5-HT_{2A} agonism in case of risperidone) it is hypothesized that pimavanserin, a more selective 5-HT_{2A} inverse agonist/antagonist, may be effective in the treatment of irritability and other ASD symptoms.

1.4.1 **Rationale for Study Design**

Based on the precedent of the two atypical antipsychotics approved for treatment of irritability associated with ASD, this is a 6-week, Phase 2, fixed dose, randomized,

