2.4.1 Pharmacokinetic Endpoints

- Plasma concentrations of pimavanserin, and AC-279
- Pimavanserin PK parameters such as, but not limited to, C_{max} and AUC, using a population PK approach

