6.5 Pharmacokinetic Assessments

At each predefined timepoint, PK samples will be obtained for measurement of concentrations of pimavanserin and its metabolite AC-279. When possible, an additional PK sample will be collected from subjects at any ET visit, or who experience a serious adverse event (SAE) or an adverse event (AE) leading to discontinuation, as soon as possible after the occurrence of that event.

For all PK samples (scheduled and unscheduled), the dates and times of administration of the last three doses of the study drug should be recorded. For samples collected from subjects who experience an SAE or an AE leading to discontinuation, the date and time of the last dose prior to the SAE or AE should also be recorded.

Pimavanserin and AC-279 plasma concentration data will remain blinded until the unblinding of the clinical database at the end of the study.

At the Baseline visit, a PK sample is drawn predose.

At Visit 3, Visit 5, Visit 8, or upon ET, a single PK sample will be collected at each visit within one of the following time intervals:

- 1-3 hours after dosing
- 4-7 hours after dosing
- 8-11 hours after dosing

Every effort should be made to collect a PK sample within each of the specified time intervals (1-3 hours after dosing, 4-7 hours after dosing, and 8-11 hours after dosing) over the course of the study visits that require a PK sample collection.

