5 GENERAL CONSIDERATIONS FOR DATA ANALYSES

5.1 Data Presentation Conventions

For continuous variables, the following summary statistics will be provided: number of subjects, mean, standard error of the mean (SE), standard deviation (SD), minimum, maximum, and median. Unless specified otherwise, means, medians, and confidence intervals (CIs) will be presented to one more decimal place than the raw data, and the SDs and SEs will be presented to 2 more decimal places than the raw data. Unless otherwise specified, the maximum number of

decimal places is 4 and values will be truncated to 4 decimal places in situations where there are more than 4 decimal places. Wherever possible data will be decimal aligned.

For categorical variables, summaries will include the number and percentage of subjects in each category. For demographic and baseline characteristics, the number of subjects and the percentage of subjects with missing data will be summarized (if applicable), and the denominator for percentages will be the total number of subjects in the given treatment group, unless otherwise specified. Categories with zero counts will not have zero percentages displayed. Percentages will be presented to 1 decimal place.

All data captured in the Electronic Data Capture (EDC) system will be presented in the listings.

Unless specified otherwise, all statistical tests will be 2-sided hypothesis tests performed at the significance level of 0.05 for main effects and all confidence intervals (CIs) will be 2-sided 95% CIs. P-values will generally be presented to 4 decimal places; values less than 0.0001 will be presented as <0.0001.

Values that are collected with "<" or ">" signs will generally be analysed as the numerical value without the sign in tables and figures. In listings, these data will be reported as collected with the sign.

Duration in years is calculated as number of days/365.25 and will be rounded to 1 digit after the decimal point (tenths) for presentation purposes.

Duration in months is calculated as (number of days/365.25)×12 and will be rounded to 1 digit after the decimal point (tenths) for presentation purposes.

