5.3.2 Analysis Visit Windows

The Baseline value is defined as the most recent non-missing value collected prior to the administration of the first dose.

Efficacy, safety and PK assessments will be summarized by analysis visits as presented in Table 1 below.

Table 1 Analysis Visit Windows

Analysis Visit Name	Target Study Day	Study Day Interval
Baseline	1	≤1
Week 1	8	2 to 11
Week 2	15	12 to 18
Week 3	22	19 to 25
Week 4	29	26 to 32
Week 5	36	33 to 39
Week 6	43	≥40

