5.3.3 Unscheduled Assessments

Both scheduled and unscheduled assessments, including early termination visits, will be considered for planned timepoint analyses based on the above analysis visit windowing rules. All assessments will be presented in data listings.

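### The SAP puts plasma concentrations into weekly rows by study day with no time-since-last-dose condition, so a sample drawn after dosing stopped can enter the Week 1, 3 or 6 summary

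*SAP*

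**What the plan says.** - Protocol 2.4.1 makes "Plasma concentrations of pimavanserin, and AC-279" a PK endpoint. SAP 15 commits to a descriptive output: "Plasma concentration data for pimavanserin and its metabolite (AC-279) will be listed and summarized using standard summary statistics". It gives no visits, no grouping and no limit on time since the last dose.
- SAP 5.3.2 brings PK under the general windows: "Efficacy, safety and PK assessments will be summarized by analysis visits as presented in Table 1 below". Table 1 sets Week 1 as days 2-11, Week 2 as 12-18, Week 3 as 19-25, Week 4 as 26-32, Week 5 as 33-39, and Week 6 as day 40 onward with no upper limit.
- SAP 5.3.3 adds: "Both scheduled and unscheduled assessments, including early termination visits, will be considered for planned timepoint analyses based on the above analysis visit windowing rules". Under SAP 5.3.4, if several continuous values share a post-baseline window and one is needed, the value nearest the target day is used. Dosing is not mentioned.
- The PK Analysis Set (SAP 4) selects subjects with at least one measurable concentration. It does not screen individual samples.
- Protocol Table S-1 and 6.5 schedule PK at Baseline (predose) and Visits 3, 5 and 8 (Weeks 1, 3 and 6). Where possible, "an additional PK sample will be collected from subjects at any ET visit", and also after a serious adverse event or an adverse event leading to discontinuation.
- Protocol 6.5 asks that the Visit 3, 5, 8 and ET samples fall in one of three post-dose intervals between 1 and 11 hours. It also has the times of the last three doses recorded.
- SAP 5.1 says that results carrying a '<' or '>' sign "will generally be analysed as the numerical value without the sign in tables and figures".

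**The concern.** A reader takes the Week 3 row of a concentration table as exposure while on drug at Week 3. The windowing rule does not guarantee that. It was written for all efficacy, safety and PK data together and looks only at the calendar. For PK, the decisive variable is time since the last dose, and the rule ignores it.

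Three things follow:

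- A post-discontinuation level can be counted as Week-N exposure.
- Such a level can replace a valid on-drug sample from the same subject.
- Weeks 2, 4 and 5 have windows but no scheduled PK sample.

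The sign rule raises a separate issue at Baseline, where the true concentration before the first dose should be nil. What is at stake is how faithfully the descriptive table represents a stated PK endpoint.

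**Working it through.** **1. The plan's own figures.** With a difference of 5 and SD of 10, a two-sided t-test at 0.05 has power 0.795 at 63 per arm and 0.801 at 64, so 64 is reproduced. Then 64/(1 - 0.15) = 75.3, rounded up to 76. This implies up to 76 - 64 = 12 discontinuations per arm.

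Protocol 1.3.2 gives half-lives of 57 h (pimavanserin) and 200 h (AC-279). Accumulation with daily dosing is 1/(1 - 0.5^(24/half-life)), which gives 3.95-fold and 12.5-fold. The protocol reports about 3- to 5-fold and 13- to 18-fold. The half-lives are good enough for a rough calculation.

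**2. Where scheduled samples land.** Target days 8, 22 and 43, each plus or minus 3 days, give days 5-11 (Visit 3), 19-25 (Visit 5) and 40-46 (Visit 8). These map only to Weeks 1, 3 and 6. Any Week 2, 4 or 5 row, if produced, would hold only ET, event-triggered or out-of-window samples.

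**3. Displacement.** Take a Visit 5 sample on Day 19 and an ET sample on Day 23. Both are in the Week 3 window (target Day 22), at distances of 3 days and 1 day. SAP 5.3.4 selects Day 23, even if dosing had stopped by then.

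**4. Level after the last dose.** Fraction remaining = 0.5^(24d/half-life), with d in days. The values of d are assumptions; the documents give no gap. Continued formation of AC-279 from parent is ignored.

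| Days off drug | Pimavanserin | AC-279 |
|---|---|---|
| 1 | 75% | 92% |
| 3 | 42% | 78% |
| 7 | 13% | 56% |
| 14 | 2% | 31% |

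**5. How many ET samples.** Assume 12 discontinuations per arm spread evenly over days 2-42 (41 days), all with an ET sample. The expected count is 12 × (days in window)/41:

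- Week 1: 12 × 10/41 = 2.9
- Weeks 2, 3, 4 and 5: 12 × 7/41 = 2.0 each
- Week 6: 12 × 3/41 = 0.9

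**6. Effect on the scheduled-visit means.** With n on-drug values and k off-drug values at fraction f, the mean changes by (n + kf)/(n + k) - 1. The range covers 3 to 14 days off drug.

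| Row | n, k | Pimavanserin | AC-279 |
|---|---|---|---|
| Week 1 | 73, 2.9 | -2.2% to -3.8% | -0.8% to -2.6% |
| Week 3 | 70, 2.0 | -1.6% to -2.7% | -0.6% to -1.9% |
| Week 6 | 64, 0.9 | -0.8% to -1.4% | -0.3% to -1.0% |
| Week 6, extreme: all 12 land here | 64, 12 | -9.2% to -15.5% | -3.5% to -10.9% |

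**7. Spread across the post-dose intervals.** From 1 h to 11 h, elimination alone leaves 0.5^(10/57) = 0.885 of pimavanserin and 0.5^(10/200) = 0.966 of AC-279. Pooling the three intervals therefore costs about 11% and 3% at most on this basis.

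**8. Sign rule.** If the laboratory reports a predose sample as '<LLOQ', dropping the sign enters the LLOQ itself. A Baseline group made up of such results would have a mean equal to the LLOQ. No LLOQ or PK reporting convention is given, so this cannot be sized.

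**The case against.** The strongest reply has four parts.

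- **Collection is tied to dosing.** Protocol 6.5 asks for ET samples in the same post-dose intervals as scheduled ones, and Protocol 3.1.3 places the ET visit at the time of discontinuation. A serious adverse event need not stop treatment. Full withdrawal of consent produces no ET visit.
- **The extra weekly rows are not promised.** SAP 5.3.3 refers to planned timepoints, SAP 15 lists none, and SAP 1 leaves table layouts to another document. For laboratory data, SAP 14.2.1.1 tabulates only Baseline, Week 3 and Week 6 although the same windows apply.
- **Exposure is estimated elsewhere.** Cmax and AUC come from population PK, reported separately, and the recorded dose times are available for that work.
- **The sign rule is hedged.** SAP 5.1 says only that it applies generally.

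Most of this stands as a limit on size. A reader might infer that the Week 2, 4 and 5 rows would contain nothing but off-drug levels. The documents do not support that: some of those samples may be on drug, and the rows themselves are only inferred. A reader might also infer that the PK objective cannot be met. That does not follow either, because the expected shift in the scheduled rows is a few percent and population PK is separate. The SAP and Protocol 9.5.4 make population PK conditional on the data; the protocol synopsis does not.

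The reply does not remove the rule. A requested collection interval is not a selection criterion, and SAP 5.3.2 names PK explicitly. Nothing in SAP 4 or SAP 15 would exclude an ET sample drawn days after the last dose.

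**Conclusion.** The concern holds in a limited form and is minor. As written, the SAP can place a post-discontinuation concentration in the Week 1, 3 or 6 summary, or let it displace an on-drug value. An individual value could be far off, but the expected fall in the scheduled-visit pimavanserin means is roughly 1-4%. That rests on discontinuation at the planned maximum of 15%, spread evenly, with every discontinuer giving an ET sample 3 to 14 days off drug. These assumptions lean towards overstating the effect, apart from even spread. If all 12 ET samples fell in the open-ended Week 6 window, the fall would be about 9-16%. Only the descriptive concentration summary is affected. The Baseline distortion depends on the laboratory reporting '<LLOQ', which the documents do not settle.

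**What to change.** In SAP 15, exempt PK from SAP 5.3.2 to 5.3.4 and from the sign rule in SAP 5.1, and state the following:

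- Tabulate the scheduled Baseline (predose) samples, and the scheduled Week 1, 3 and 6 samples taken within the protocol's 1-11 h post-dose intervals, as judged from the recorded dose times.
- Show results by mg dose and age stratum within arm. Each active arm contains two mg doses, and 20 mg occurs in both arms.
- Give one rule for all values below quantification, for example predose values set to zero, with the treatment of post-dose values also stated.
- List ET and event-triggered samples separately with time since last dose.

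A further split by post-dose interval is not needed. It would make 3 visits × 2 active arms × 2 age strata × 3 intervals = 36 cells. At the minimum of 80 younger children, about 80/3 = 27 per arm, that leaves roughly 27/3 = 9 per cell before dropout, to remove a spread of about 11%.

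The cost is SAP wording, revised table shells and slightly fewer values per summary. No new data are required.
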